5.2. Pre-Treatment Criteria

N/A

5.3. Agent Administration

5.3.1. CTEP and/or CIP IND Agent(s), or other IND agent

N/A

5.3.2. Other Agent(s)

Perampanel:

Each perampanel dose will be a single tablet taken by mouth once a day. A loading dose of 6mg will be administered 12-36 hours prior to planned surgery start time. Maintenance dosing of 4mg will start 24 hours after the loading dose, and continued daily. Perampanel may be administered with or without food. It should not be crushed, chewed, or dissolved. Doses should be retaken if missed or vomited. There is no specific observation period required. There are no specific caregiver precautions.

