5. TREATMENT PLAN

5.1. Treatment Regimen

Perampanel will be given every day until meeting the study endpoint(s). Reported adverse events and potential risks are described in Section 7. Appropriate dose modifications are described in Section 6. Other anti-seizure medication(s) may be administered during perampanel maintenance therapy as clinically indicated.

Cohort 1

Participants who are already receiving an anti-seizure medication pre-operatively for treatment of tumor-associated seizures will receive their last dose at least 36 hours before scheduled surgery start-time, and then will be switched to perampanel. The loading dose of perampanel will be 6mg by mouth, given on the day prior to surgery (12-36 hours before scheduled start time), followed by a maintenance dose of 4mg by mouth once a day. Participants will be requested to maintain a drug diary of each dose of medication. The drug diary will be returned to clinic staff at the end of each month.

Study day	Perampanel dose
Day 1 (load)	6mg
Day 2+ (maintenance)	4mg

Cohort 2

Perioperative and post-operative seizure management will be performed by the primary treating physician(s) according to institutional standards.

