6. DOSING DELAYS/DOSE MODIFICATIONS

Perampanel dose modifications are permitted as clinically indicated to optimize seizure control and minimize adverse effects. Dose adjustment may be performed by the primary treating neurologist and/or study investigators. For any adjustment, the Principal Investigator, [name], will be notified. A maximum daily maintenance dose for this study will be 8mg.

At the completion of the study, if perampanel is not clinically indicated and/or planned to be withdrawn, the daily dose will be tapered down by 2mg per week to the minimum therapeutic dose of 4mg, then stopped. If perampanel is being discontinued for lack of seizure efficacy, an alternative anti-seizure medication chosen at the discretion of the primary treating neurologist will be started and titrated to a therapeutic dose, after which perampanel will be tapered off as above. If the participant experiences a serious adverse event attributed to perampanel, the drug may be stopped immediately if, at discretion of the Principal Investigator, the benefits outweigh the risks.

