7.3. Adverse Event Reporting

7.3.1. In the event of an unanticipated problem or life-threatening complications treating investigators must immediately notify the Overall PI.

7.3.2. Investigators **must** report to the Overall PI any adverse event (AE) that occurs after the initial dose of study treatment, during treatment, or within 30 days of the last dose of treatment on the local institutional SAE form.

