11.1.7. Response Review

Review of MRI or CT scans will be performed by [name] or his designee.

11.2. **Seizure Response**

Seizure response will be evaluated every 4 weeks for the secondary endpoint of time to seizure recurrence, measured from the date of surgery. Seizure frequency will be monitored using a seizure diary form completed by participants and reviewed every 4 weeks. Baseline seizure frequency will be defined by the number of clinical seizures reported by participants in the month preceding surgery. Seizure freedom is defined by the absence of seizures.

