13.7. Reporting and Exclusions

13.7.1. Evaluation of Toxicity

All participants will be evaluable for toxicity from the time of their first treatment.

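### For Cohort 1 participants already on an anti-seizure drug, nothing ties the perampanel load to the last dose of the old drug, so the plan permits 24 hours or more with no dose

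*Combined protocol and SAP*

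**What the plan says.** Section 5.1 applies a switch rule to Cohort 1 participants who are already treated for tumor-associated seizures. They "will receive their last dose at least 36 hours before scheduled surgery start-time, and then will be switched to perampanel". The 6 mg load is "given on the day prior to surgery (12-36 hours before scheduled start time"), and Section 5.3.2 repeats the window: "A loading dose of 6mg will be administered 12-36 hours prior to planned surgery start time". Neither section links the load to the last dose of the old drug or limits how early that drug may stop. Section 5.1 allows other anti-seizure drugs during perampanel maintenance, but says nothing about the time before the load.

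Section 3.2.10 excludes anyone on more than one anti-seizure drug, and Section 3.2.9 excludes anyone whose tumor-associated seizures go back more than a month. Cohort 2 is managed by its treating physicians to institutional standards.

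On safety data, Section 7.3.2 requires reports to the overall investigator of "any adverse event (AE) that occurs after the initial dose of study treatment", and Section 13.7.1 says "All participants will be evaluable for toxicity from the time of their first treatment".

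**The concern.** The people affected had tumor-associated seizures within the past month and take a single drug for them. The protocol withdraws that drug on a clock that runs back from surgery, and starts the replacement on a second, looser clock. A site can follow both rules exactly and still leave a participant a day or more without any anti-seizure dose. Only Cohort 1 is exposed to this by protocol.

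Two of the safety rules start at the first study dose. A seizure after the old drug is stopped and before the load has no clearly stated place in the safety record, although it would be the event most directly linked to the switch.

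**Working it through.** The plan gives no figure for this interval, so there is none to reproduce. The check is time arithmetic.

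Inputs:
- S, hours from the last dose of the old drug to scheduled surgery: 36 or more (5.1). S = 48 is used as an illustration of an earlier stop.
- L, hours from load to surgery: 12 to 36 (5.1, 5.3.2).
- τ, dosing interval of the old drug: not given. Assumed 8, 12 or 24 hours.
- Time to perampanel peak: 0.5-2.5 hours fasted, delayed by 1-3 hours when fed (8.1.1), so at most 2.5 + 3 = 5.5 hours.

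**Dose-free interval, S − L (hours):**

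| Load at L = | 36 | 24 | 18 | 12 |
|---|---|---|---|---|
| S = 36 | 0 | 12 | 18 | 24 |
| S = 48 | 12 | 24 | 30 | 36 |

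The interval is zero only if both doses fall at 36 hours. Section 5.1 also puts the load on the day before surgery. For an assumed 8am start that day begins 32 hours before, so the shortest interval is then 36 − 32 = 4 hours.

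**Time past the next due dose, max(0, S − L − τ), for τ = 8, 12, 24:**
- S = 36, L = 12: 16, 12, 0 hours.
- S = 36, L = 24: 4, 0, 0 hours.
- S = 48, L = 12: 28, 24, 12 hours.

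**Last old dose to perampanel peak, S = 36, L = 12:** 24 + 0.5 = 24.5 to 24 + 2.5 = 26.5 hours fasted, and up to 24 + 5.5 = 29.5 hours fed.

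**How many participants:** the documents do not say. If the upper figure of 60% with seizures in Section 2.1 applied to Cohort 1 and all were treated, it would be 0.60 × 10 = 6 of 10. A lower share gives fewer.

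**Check of the proposed rule.** A load no later than the next due dose and inside the window is possible when S − τ ≤ 36. At S = 36 the next dose is due 28, 24 or 12 hours before surgery for τ = 8, 12, 24, all inside the window. At S = 48 it is due at 40, 36 or 24 hours, so an 8-hourly drug would need its last dose at 36-44 hours.

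**Reporting rules side by side.** Sections 7.3.2 and 13.7.1 start at the first study dose. Section 7.5 asks for all adverse events in routine submissions and Section 7.3.1 for immediate notice of life-threatening or unanticipated problems, neither with a start point. The calendar's adverse event row begins in the pre-surgery column, without a time. Section 7.3.4 removes hospitalization for seizure from expedited reporting but keeps it in routine reporting. Coverage of the interval is therefore partial and its start undefined.

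**The case against.** The strongest reply is that 24 hours is a corner case. With a 36-hour stop it occurs only at the 12-hour limit of the load, and it is counted from the last dose, not from a missed one. A once-daily drug would not yet be overdue, and a twice-daily drug would have missed one dose. The text says the participant is then switched, so no gap is required. All of this stands. It does not remove the point, because the protocol permits the interval, sets no upper limit on it, and could close it with wording.

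Section 6 does secure overlap when perampanel is stopped for lack of efficacy: the replacement "will be started and titrated to a therapeutic dose, after which perampanel will be tapered off as above". But that concerns an ineffective maintenance drug, not a deliberate pre-operative washout, so the contrast is suggestive only.

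A reader might infer four stronger things, which the documents do not support:
- *Participants are unprotected for 24 hours.* The old drug's half-life and dosing interval are not given, so a gap in doses is not shown to be a gap in effect. No seizure rate for the interval is given either.
- *A late load under-doses the primary ECoG, biasing the test or lowering power.* Section 2.3 plans a single 6 mg load and says that one load can reach effective brain levels. Because "Maintenance dosing of 4mg will start 24 hours after the loading dose, and continued daily", a load more than 24 hours ahead can add a second dose before surgery. The documents give no dose-response from which to derive an effect on the HFO comparison.
- *Seizures in the interval go unreported.* Sections 7.3.1 and 7.5 and the calendar partly cover them. What is missing is a defined start.
- *Baseline seizure counts are distorted, with analytic consequences.* Section 11.2 does say "Baseline seizure frequency will be defined by the number of clinical seizures reported by participants in the month preceding surgery", but Section 13.1 does not use that frequency. It stratifies only on the presence of pre-operative seizures, which these participants already have.

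**Conclusion.** The point holds as a patient-safety gap in the dosing instructions, worth correcting because correction is cheap. For Cohort 1 participants on a previous anti-seizure drug, the plan permits a dose-free interval of 12 to 24 hours when the load is given 24 to 12 hours before surgery after a 36-hour stop, and a longer one after an earlier stop. The intervals follow directly from Sections 5.1 and 5.3.2. The overdue times rest on assumed dosing intervals, and the count of up to 6 rests on an assumed seizure prevalence. No number of seizures is claimed.

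**What to change.** In Sections 5.1 and 5.3.2, for participants on a previous drug, give its last dose 36-48 hours before scheduled surgery and the 6 mg load no later than that drug's next due dose, within the existing 12-36 hour window. For an 8am start and a twice-daily drug, the last dose is at 8pm two evenings before and the load at 8am the day before. For an 8-hourly drug the last dose should be at 36-44 hours. In Sections 7.3.2 and 13.7.1, start adverse event recording for these participants, seizures included, at the last dose of the previous drug.

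The 36-hour washout, doses, sample size, endpoints and tests are unchanged. The cost is an earlier load on the day before surgery for some participants on a previous drug. They need no extra recruitment lead time, because Section 4.1 already requires registration before any protocol intervention, and so before the stop. A load at exactly 24 hours makes the first 4 mg dose due at the scheduled start, as the current window also allows. The protocol should say whether it is then given before or after surgery. Participants on no previous drug are unaffected.

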5.3.3. Other Modality(ies) or Procedures

Electrocorticography (ECoG):

Intraoperative electrocorticography (ECoG) will be performed for 10 minutes using an Xltek machine (Natus Medical Inc, Pleasanton, CA), sampled at 1000 Hz per channel, with a subdural 4x5 electrode grid overlying the tumor margins, according to institutional clinical protocols. At least 10 minutes prior to ECoG, inhaled anesthetics and propofol infusion will be stopped, as per standard institutional practices. Subsequent tumor resection will be performed at the discretion of the neurosurgeon, and high frequency activity will be analyzed independently post-operatively (see Section 9.1).

5.3.4. Investigational Imaging Agent Administration

N/A

5.4. General Concomitant Medication and Supportive Care Guidelines

Because there is a potential for interaction of perampanel with other concomitantly administered drugs through the cytochrome P450 system, the case report form must capture the concurrent use of all other drugs, over-the-counter medications, or alternative therapies. The Overall PI should be alerted if the participant is taking any agent known to affect or with the potential to affect selected CYP450 isoenzymes. Appendix C presents guidelines for identifying medications/substances that could potentially interact with the study agent(s).

5.5. Criteria for Taking a Participant Off Protocol Therapy

Duration of therapy will depend on individual response, evidence of disease progression and tolerance. In the absence of treatment delays due to adverse event(s), treatment may continue for 12 months or until one of the following criteria applies:

- Intercurrent illness that prevents further administration of treatment
- Unacceptable adverse event(s)
- Participant demonstrates an inability or unwillingness to comply with the oral medication regimen and/or documentation requirements
- Participant decides to withdraw from the protocol therapy
- General or specific changes in the participant's condition render the participant unacceptable for further treatment in the judgment of the treating investigator

Participants will be removed from the study protocol when any of these criteria apply. The reason for removal from protocol, and the date the participant was removed, must be documented in the case report form (CRF). Alternative care options will be discussed with the participant. Perampanel may be continued on a clinical basis by the primary treating physician. If the participant is taken off protocol for active suicidal ideation with intent (defined by the Columbia Suicide Severity Rating Scale Type 4-5), the Principal Investigator will arrange for immediate psychiatric evaluation.

When a participant is removed from protocol therapy and/or is off of the study, the participant's status must be updated in OnCore in accordance with [REGIST-OP-1](#).

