1.2 Secondary Objectives

Secondary Objective: Estimate the clinical effect of perampanel maintenance therapy on seizure control. We will measure seizure-free rates between the time of initial glioma resection and radiographic tumor progression (up to a maximum of 12 months), in participants continued on perampanel post-operatively (Cohort 1) compared to control participants (Cohort 2).

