5.6. Duration of Follow Up

Participants will be followed as clinically indicated after removal from protocol or until death, whichever occurs first. Participants removed from protocol therapy for unacceptable adverse event(s) will be followed until resolution or stabilization of the adverse event. After completion of the study, if the treating neurologist cannot be contacted or the participant no longer wishes to see their treating neurologist, the principal investigator will help the participant to transition care to a different treating neurologist and will follow them clinically until then.

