5.7. Criteria for Taking a Participant Off Study

Participants will be removed from study when any of the following criteria apply:

- Disease progression
- Lost to follow-up
- Withdrawal of consent for data submission
- Death

The reason for taking a participant off study, and the date the participant was removed, must be documented in the case report form (CRF). In addition, the study team will ensure the participant's status is updated in OnCore in accordance with [REGIST-OP-1](#).

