13.1. Study Design/Endpoints

Pilot Study: Preliminary Study

- Primary objective: Compare rates of peritumoral HFOs (mean number of HFOs per minute) between participants treated with perampanel versus standard of care.
- Secondary objective: Compare time to seizure recurrence between participants treated with perampanel versus standard of care up to the time of HGG progression.
- Maximum total accrual: 10 participants in Cohort 1, 10 participants in Cohort 2.
- Sample size justification: Using the mean HFO rate across participants receiving standard of care (Cohort 2) as the normalized ineffective rate ($P_1=1.0$), we define a target effective rate for the treatment arm (Cohort 1) of $P_2=0.60$. Using a two sample power calculation, the intended sample size of 10 participants in each cohort will provide 82.5% power to detect a true 40% or greater reduction in the normalized mean HFO rate with perampanel compared to standard of care ($\alpha=0.05$, two-sided).
- Statistical methods for primary objective: The primary endpoint is the mean number of HFOs per minute. This will be averaged across participants in each cohort, and compared using the Mann-Whitney U test (two-sided, $\alpha=0.05$). In sensitivity analyses, we will compare HFO rates between cohorts stratified by potential confounding variables, including temporal lobe tumor location, IDH1/2 mutation, and pre-operative seizures.
- Statistical methods for secondary objective: The secondary endpoint is the time to first post-operative seizure. Time to first post-operative seizure will be estimated in time-to-event analysis from the date of surgery using the Kaplan-Meier method. Comparison

between Cohort 1 and Cohort 2 will be performed using the log-rank test ($\alpha=0.05$). In sensitivity analyses, we will compare time to first post-operative seizure between cohorts stratified by potential confounding variables, including temporal lobe tumor location, extent of resection (gross total vs subtotal resection), presence of IDH1/2 mutation, and presence of pre-operative seizures.

- Data processing and statistical analysis will be performed using R 3.5.3 (The R Foundation for Statistical Computing).
- These results will be used to support or refute the hypothesis that perampanel has targeted anti-epileptogenic activity in glioma-associated epilepsy, and may inform the design and feasibility of future clinical studies of targeting the glutamatergic pathway in this patient population.

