13.7.2. Evaluation of the Primary Efficacy Endpoint

All participants in Cohort 1 who receive at least one dose of study treatment and all participants in Cohort 2 will be evaluable for response.

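### Sections 5.5 to 5.7 leave open whether seizure data are still collected after perampanel stops, and no analysis set or censoring rule covers this for the secondary endpoint

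*Combined protocol and SAP*

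**What the plan says.** Section 5.5, whose heading concerns protocol therapy, lists intercurrent illness, unacceptable adverse events, non-compliance, the participant's own decision, and a change in condition. It then states: "Participants will be removed from the study protocol when any of these criteria apply". One criterion reaches beyond the drug itself: "Participant demonstrates an inability or unwillingness to comply with the oral medication regimen and/or documentation requirements".

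Section 5.6 sets what happens next: "Participants will be followed as clinically indicated after removal from protocol or until death, whichever occurs first". It gives no schedule for seizure assessment.

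Section 5.7 has its own list, introduced by "Participants will be removed from study when any of the following criteria apply". The list is progression, loss to follow-up, withdrawal of consent for data submission, and death. Stopping perampanel is not on it.

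For the analysis, section 1.2 words the seizure comparison as one "in participants continued on perampanel post-operatively (Cohort 1) compared to control participants (Cohort 2". Section 13.1 states "The secondary endpoint is the time to first post-operative seizure", estimated by Kaplan-Meier from the date of surgery and compared between the two cohorts by log-rank test. Section 13.6 only refers back to 13.1. Section 13.7.2, under the primary endpoint heading, says: "All participants in Cohort 1 who receive at least one dose of study treatment and all participants in Cohort 2 will be evaluable for response". Section 11.2 supplies the data through a diary reviewed every 4 weeks.

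**The concern.** The 4-weekly diary is the source of the secondary endpoint. A site that follows 5.5 and 5.6 to the letter may stop collecting it once a participant comes off perampanel. Cohort 2 receives usual seizure management, so a control who stops or switches an anti-seizure drug triggers no removal. Follow-up would then depend on a post-baseline event in essentially one cohort.

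The analyst would also have to choose between excluding such participants, censoring them at the stop, and following them on. The plan does not choose, and these options can give different answers.

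Section 13 says the secondary outcome is there to estimate an effect size, and section 13.1 says the results may inform later studies. Seizure data that were never collected cannot be recovered at analysis.

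**Working it through.** The plan states no figure for the secondary endpoint. Its 82.5% power is for the primary HFO comparison and does not bear on this point.

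**Step 1. The sections side by side.**

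| Question | Points to data ending at removal | Points to data continuing |
|---|---|---|
| Is someone who stops perampanel still in the study? | 5.5, closing rule: removed from the protocol | 5.5, heading: therapy only; 5.7: drug stop not an off-study reason |
| Is the diary still due? | 5.6: clinically indicated follow-up only | 11.2: every 4 weeks, no exception stated |
| Who is compared? | 1.2: Cohort 1 participants continued on drug | 13.1: whole cohorts; 13.7.2: at least one dose, but for the primary endpoint |

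No section states the secondary analysis set or a censoring rule for stopping perampanel.

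**Step 2. How often it could arise.** Section 2.3 cites 3% discontinuation for adverse effects at 4 mg; the other removal reasons are not quantified. With 10 in Cohort 1:
- At 3%: expected stops 10 × 0.03 = 0.3; chance of at least one 1 − 0.97^10 = 26%.
- At an assumed 10%: 1 − 0.90^10 = 65%.
- Each participant is 1/10 = 10 percentage points of the cohort.

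**Step 3. Size if only continuers are analysed.** Assumptions, not document figures: 60% of continuers are seizure-free at 12 months; a fraction p stops; stoppers have m times the seizure hazard throughout, so 0.60^m of them are seizure-free (0.36 for m = 2, 0.216 for m = 3). The true rate in all treated is (1 − p) × 0.60 + p × 0.60^m.

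| p | m | True rate | Continuers only | Error |
|---|---|---|---|---|
| 3% | 2 | 0.97×0.60 + 0.03×0.36 = 59.3% | 60% | +0.7 |
| 3% | 3 | 0.97×0.60 + 0.03×0.216 = 58.8% | 60% | +1.2 |
| 10% | 2 | 0.90×0.60 + 0.10×0.36 = 57.6% | 60% | +2.4 |
| 30% | 3 | 0.70×0.60 + 0.30×0.216 = 48.5% | 60% | +11.5 |

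**Step 4. Size if stoppers are censored at the stop.** Same assumptions, with stop times uniform over 0 to 6 months. Let λ = −ln(0.60)/12 per month, a(t) = (1 − p)e^(−λt), and b(t) = p e^(−mλt)(1 − t/6) up to month 6 and 0 after. The Kaplan-Meier curve follows the hazard λ(a + m b)/(a + b). Integrating to 12 months:
- p = 3%: 59.8% (m = 2) and 59.6% (m = 3), errors +0.5 and +0.8.
- p = 10%, m = 2: 59.3%, error +1.7.
- p = 30%, m = 3: 55.7%, error +7.2.

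**Step 5. A milder link.** A separate simulation with no drug effect assumed true seizure-free rates of 0.70 or 0.50 and 10% or 30% stopping. The high-risk half had three times the seizure hazard and three times the stopping hazard.
- Censoring at the stop: 0.702 and 0.712 against 0.70; 0.504 and 0.517 against 0.50. At most about 2 points in favour of perampanel.
- Keeping only those who never stop: 0.707 and 0.723; 0.509 and 0.532. At most about 3 points in favour.
- Censoring when stopping is unrelated to risk: no bias.

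**Step 6. The direction can reverse.** Suppose those who stop before a first seizure are dropped, and stopping is unrelated to risk. With 50% seizure-free and 30% stopping, constant hazards over 12 months are ln 2 = 0.693 and −ln(0.70) = 0.357. Kept and seizure-free: 0.50 × 0.70 = 0.350. Kept with a seizure: 0.693/(0.693 + 0.357) × (1 − 0.350) = 0.429. The estimate is 0.350/(0.350 + 0.429) = 0.449 against a true 0.50, about 5 points against perampanel.

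**The case against.** The strongest reply is that the plan uses the usual split between off-therapy and off-study. Section 5.5 is about therapy, 5.7 has its own list without drug stop, and 11.2 asks for 4-weekly seizure evaluation without exception. On that reading one sentence in 5.5 is loosely worded and the diary simply continues. The wording in 1.2 can be read as describing what Cohort 1 receives, and the operative text in 13.1 compares whole cohorts. This is a fair reading, and it is why the plan cannot be said to exclude anyone. It does not remove the problem: the closing rule in 5.5 and the follow-up sentence in 5.6 say something else, and a site could follow them.

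Other points stand in full. A stop prompted by a seizure comes after the endpoint event, which limits the bias. Removal is not the same as stopping the drug, since 5.5 allows perampanel to continue clinically off protocol. The documents support no stopping rate above 3%, though that figure covers adverse effects only. The endpoint is exploratory, in a preference-allocated pilot of 10 per cohort. With an assumed 10 events, log-rank power at a hazard ratio of 0.5 is Φ(√10/2 × 0.693 − 1.96) = 19%. Low precision limits the consequence but does not justify losing data from one cohort.

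**Conclusion.** The point holds as an inconsistency that can cost secondary-endpoint data unequally. Taken literally, 5.5 and 5.6 end scheduled seizure follow-up mainly for Cohort 1 participants who stop perampanel; only the documentation criterion could reach Cohort 2.

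A reader might go further and infer that the plan drops stoppers from the analysis, keeps all of Cohort 2 in, and so certainly biases the result. The documents do not support that. No section excludes stoppers, 13.1 compares cohorts, and Cohort 2 also leaves under 5.7. Bias arises only if stopping is related to seizure risk or if stoppers are excluded.

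Its size and sign depend on unstated handling and on assumptions: about 1 point at the cited 3% with a two- to threefold hazard in stoppers, and more at higher assumed rates. The 11.5-point case needs 30% stopping, a threefold hazard from the start and complete exclusion of stoppers, none of which the documents state. Excluding those who stop before a first seizure can shift the estimate about 5 points the other way. The primary HFO endpoint, measured at surgery, is not affected by post-operative stopping.

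**What to change.** - **Sections 5.5 and 5.6:** state that stopping perampanel ends protocol therapy only. Seizure diary and monthly contact continue in both cohorts until progression, death, withdrawal of consent for data submission, loss to follow-up, or 12 months. Reconcile 5.5 with 5.7 accordingly.
- **Sections 1.2 and 13.1:** define the secondary analysis set as all Cohort 1 participants with at least one dose and all Cohort 2 participants, regardless of later perampanel use. This extends the set in 13.7.2 to the secondary endpoint.
- **Section 13.1:** state censoring at progression, last contact or 12 months. Report censoring at drug stop only as a sensitivity analysis.

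The sample size, alpha and primary power statement do not change, and neither do the clinical criteria for stopping perampanel. The cost is protocol wording plus continued monthly phone contact, already allowed for in the section 10 calendar, for the few who stop.
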